9. MATURATION OF MEDAMACS

The launching of MedaMACS will focus on the ambulatory population closely proximal to the common threshold for implementation of mechanical circulatory support. The foundation of the 10 sites entering patients for the MedaMACS screening pilot will allow rapid initiation of the new protocol, with the additional 2 sites. The fastidious definition of entry criteria offers a fine-tuning knob to dial up or down disease acuity of patients enrolled, as this becomes necessary. However, the general approach to baseline data collection, risk profiling, assessment of adverse events and outcomes, is planned for cascading applications to progressively "more well" populations to keep pace with those enrolling into INTERMACS. The next promising target population will be the population of patients waiting at home after listing for transplant. As the improving outcomes of implantable VADs are demonstrated by INTERMACS to advance beyond a bridge to transplant, past even the current focus on the transplant-ineligible population, MedaMACS will prepare the field on which mechanical circulatory support will finally compete with cardiac transplantation as primary therapy to improve quality life for a substantial proportion of the patients currently suffering from advanced heart failure.

APPENDIX A: SURVEY INSTRUMENTS

Part I: Physician Questionnaire:

Baseline A only

- 1. How long has patient been under care of your heart failure program?
 - $A_{\cdot} < 3$ months
 - B. 3-12 months
 - C. 1-2 years
 - D. > 2 years
- 2. If <3 months, which best describes the route of presentation: (as a drop-down from A in previous)
 - A. New onset event or diagnosis within your institution
 - B. Unspecified evaluation of severe heart failure
 - C. Cardiac transplant and/or VAD evaluation
- 3. If a referral (B or C above), who referred the patient? (as a drop-down from B/C in previous)
 - A. Local internist
 - B. Local cardiologist
 - C. Cardiac Surgeon
 - D. Self-referral
 - E. Unsure
 - F. Other

Baseline A, B, 12 months and 24 months: (face to face encounters)

4. What is your best estimate of the likelihood of becoming sick enough to warrant urgent Stage D intervention within one year? This includes home inotropes, hospice, VAD, and urgent transplant.

- A. Highly LIKELY
- B. Moderately LIKELY
- C. Uncertain
- D. Moderately UNLIKELY
- E. Highly UNLIKELY

5. If it became medically indicated, what is likelihood that this patient would be eligible for transplant?

- A. Highly LIKELY
- B. Moderately LIKELY
- C. Uncertain
- D. Moderately UNLIKELY
- E. Highly UNLIKELY

6. If a VAD became medically indicated, what is the likelihood that they would require biventricular mechanical support rather than LVAD alone?

(answer only if C, D, E in question 5)

- A. Definitely need Biventricular support
- B. Probably need Biventricular support
- C. Uncertain
- D. Probably LVAD only
- E. Definitely LVAD only

7. If not likely to be a transplant candidate and mechanical support became medically indicated, what is likelihood the patient would be eligible for destination LVAD alone as lifetime support? (answer only if C, D, E above)

- A. Highly LIKELY
- B. Moderately LIKELY
- C. Uncertain
- D. Moderately UNLIKELY
- E. Highly UNLIKELY

Part II: Patient Quality of Life Questionnaires

Baseline A, B, 12 months, and 24 months

1. Which of the following best describes your main activity?

	Actively	workir	ng			Full Ti	me 🗌 I	Part Time		
	Student	Student				Full Time 🗌 Part Time 🗌				
	Seeking	work				Full Ti	me 🗌 I	Part Time		
	Too sick	to wor	k (disat	oled)						
	Retired									
	Keeping Other (pl		pecify)							
 How many of your close friends or relatives do you see in person, speak to on the telephone, or contact via the internet at least once a month? (please count each person 1 time) 										
3. How much stress issues?	do you fee	l you'v	ve been	under	during	the past	1 month	, related t	o your health	1
1 2 No stress	3	4	5		6	7	8	9 Very muc	10 ch stress	
4. How well do you f related to your health		been o	coping v	with o	or handli	ing your	stress du	uring the p	past 1 month,	1
1		3	4	5	6	7	8	9	10	
Coping very poo	orly						Coping	very well		
5. How confident are you that you can do the tasks and activities needed to manage your heart failure so as to reduce how much having heart failure affects your everyday life?										
Not at all confide		3	4	5	6	7	8	9 Totally	10 confident	
								i oturi y	Connacht	

6. How satisfied are you with the results of your therapy for heart failure during the past 6 months? Please circle a number from 1 to 10, with 1 meaning that you're not satisfied at all, and 10 meaning that you're very satisfied.

1	2	3	4	5	6	7	8	9	10
Not	satisfied							Very sa	tisfied

EUROQOL – 5D + Thremometer

By placing a checkmark in one box in each group below, please indicate which statements best describe your own health state today.

Mobility

I have no problems in walking about	
I have some problems in walking about	
I am confined to bed	
Self-Care	
I have no problems with self-care	
I have some problems washing or dressing myself	
I am unable to wash or dress myself	
Usual Activities (e.g. work, study, housework, family or	
leisure activities)	
I have no problems with performing my usual activities	
I have some problems with performing my usual activities	
I am unable to perform my usual activities	
Pain/Discomfort	
I have no pain or discomort	
I have moderate pain or discomfort	
I have extreme pain or discomfort	
Anxiety/Depression	
I am not anxious or depressed	
I am moderately anxious or depressed	
I am extremely anxious or depressed	

Best imaginable health state

> 100 Ŧ

9**±**0

To help people say how good or bad a health state is, we have drawn a scale (rather like a thermometer) on which the best state you can imagine is marked 100 and the worst state you can imagine is marked 0.

We would like you to indicate on this scale how good or bad your own health is today, in your opinion. Please do this by drawing a line from the box below to whichever point on the scale indicates how good or bad your health state is today.

> Your own health state today

THE KANSAS CITY CARDIOMYOPATHY QUESTIONNAIRE:

The following questions refer to your **heart failure** and how it may affect your life. Please read and complete the following questions. There are no right or wrong answers. Please mark the answer that best applies to you.

Heart Failure affects different people in different ways. Some feel shortness of breath while others feel fatigue. Please indicate how much you are limited by **heart failure** (shortness of breath or fatigue) in your ability to do the following activities over the past 2 weeks.

Place an X in one box on each line									
Activity	Extremely limited	Quite a bit limited	Moderately limited	Slightly limited	Not at all limited	Limited for other reasons or did not do the activity			
Dressing yourself									
Showering/Bathing									
Walking 1 block on level ground									
Doing yard work, housework or									
carrying groceries Climbing a flight of stairs without									
stopping									
Hurrying or jogging (as if to catch a bus	s) 🗌								

1. Compared with 2 weeks ago, have your symptoms of **heart failure** (shortness of breath, fatigue or ankle swelling)

changed? My symptoms of heart failure have become

Much worse	Slightly worse	Not changed	Slightly better	Much better	I've had no symptoms over the last 2 weeks

2. Over the past 2 weeks, how many times did you have **swelling** in your feet, ankles or legs when you woke up in the morning?

Every morning	3 or more times a week, but not every day	1-2 times a week	Less than once a week	Never over the past 2 weeks

3. Over the past 2 weeks, how much has **swelling** in your feet, ankles or legs bothered you? It has been...

Extremely bothersome	Quite a bit bothersome	Moderately bothersome	Slightly bothersome	Not at all bothersome	I've had no swelling

4. Over the past 2 weeks, on average, how many times has fatigue limited your ability to do what you want?

All of the time	Several times per day	At least once a day	3 or more times per week but not every day	1-2 times per week	Less than once a week	Never over the past 2 weeks			
5. Over the past 2 weeks , how much has your fatigue bothered you? It has been									
Extremely bothersome	Quite a bit bothersome	Moderately bothersome	Slightly bothersome	Not at all bothersome	I've had no fatig	ue			

All of the time	Several times per day	At least once a day	3 or more times per week but not every day	1-2 times per week	Less than once a week	Never over the past 2 weeks

7. Over the past 2 weeks, how much has your shortness of breath bothered you?

Extremely bothersome	Quite a bit bothersome	Moderately bothersome	Slightly bothersome	Not at all bothersome	I've had no shortness of breath

8. Over the past 2 weeks, on average, how many times have you been forced to sleep sitting up in a chair or with at least 3 pillows to prop you up because of **shortness of breath**?

Every night	3 or more times a week, but not every day	1-2 times a week	Less than once a week	Never over the past 2 weeks

9. Heart Failure symptoms can worsen for a number of reasons. How sure are you that you know what to do, or whom to call, if your heart failure gets worse?

Not at all	Not very sure	Somewhat sure	Mostly sure	Completely sure
sure				

10. How well do you understand what things you are able to do to keep your **heart failure** symptoms from getting worse? (for example, weighing yourself, eating a low salt diet, etc.)

Do not understand at all	Do not understand very well	Somewhat understand	Mostly understand	Completely understand

11. Over the past 2 weeks, how much has your heart failure limited your enjoyment of life?

It has extremely	It has limited	It has	It has slightly	It has not limited my
limited my	my enjoyment	moderately	limited my	enjoyment of life

enjoyment of	of life quite	limited my	enjoyment of	at all
life	a bit	enjoyment of life	life	

12. If you had to spend the rest of your life with your **heart failure** the way it is right now, how would you feel about this?

Not at all satisfied	Mostly dissatisfied	Somewhat satisfied	Mostly satisfied	Completely satisfied

13. Over the past 2 weeks, how often have you felt discouraged or down in the dumps because of your heart failure?

I felt that way all of the time	I felt that way most of the time	I occasionally felt that way	I rarely felt that way	I never felt that way	

14. How much does your **heart failure** affect your lifestyle? Please indicate how your **heart failure** may have limited your participation in the following activities over the past 2 weeks?

Activity or did	Severely	Limited	Moderately	Slightly	Did not	Does not apply
of ala	limited	quite a bit	limited	limited	limit at all	not do for other
reasons						
Hobbies, recreationa	1					
activities						
Working or doing						
household chores						
Visiting family or fri	ends					
out of your home						
Intimate relationship	S					
with loved ones						

Please place an X in one box on each line

Developed by John Spertus et al., Mid America Heart Institute, Saint Luke's Hospital, Kansas City, MO.

Part III: MedaMACS VAD Survey

Thank you for taking the time to fill out this short survey. We will be asking you several questions about your heart failure and a new therapy for heart failure. This survey should take no more than 15 minutes of your time. Your responses will remain confidential.

1. Based on how you feel today and what you know about your heart failure, what is your

best estimate of how much longer you have to live? (choose one)

- A. Less than 6 months
- B. Between 6 months to 2 year
- C. Between 2 to 5 years
- D. More than 5 years

Ventricular Assist Device

There are many effective medical therapies available to treat congestive heart failure. Sometimes the heart can become too weak to pump enough blood to the body. At that stage, drugs may not be enough to treat heart failure.

Mechanical heart pumps called ventricular assist devices, or VADs, are a way to improve the circulation of blood throughout the body. These pumps do not replace the heart. They only assist the heart in pumping blood to the body. Once blood flow is improved, many patients have more energy and breathe easier. Clinical studies show that select patients with severe heart failure live longer with an assist device than with drug treatments alone.

Placement of a VAD requires major open heart surgery. The pump is placed inside the chest and abdomen and is connected to the heart. The VAD also has a power line that leaves the body through the skin in the front of the abdomen and is attached to a power supply outside the body. On average patients will remain in the hospital for about one month after surgery. Once discharged from the hospital, most patients are able to return home and live independently.

2. Based on how you feel right now and knowing only the above information above,

which statement best describes how you would feel about having an assist device placed?

- A. I would DEFINITELY want it
- B. I would PROBABLY want it
- C. I don't know if I would want it or not

- D. I would PROBABLY NOT want it.
- E. I would DEFINITELY NOT want it

3. Suppose that your doctor told you with certainty that you only had a limited about of time to live. The next series of questions will ask you to imagine different scenarios where you only have a certain amount of time left to live. (Check one box)

Would you want a ventricular assist device if you had:	Probably YES	Unsure	Probably NOT
A. Less than 1 month to live?	0	ο	0
B. Less than 6 months to live?	ο	ο	0
C. Less than 2 years to live?	о	0	0
D. Less than 5 years to live?	ο	0	ο

4. The next series of questions asks to imagine that you are experiencing various degrees of illness related to your heart failure. Please consider each scenario in terms of how limited you might feel and whether or not you would want an assist device to feel better. (Check one box)

Would you want an assist device if:	Probably YES	Unsure	Probably NOT
1. In the intensive care unit with hours or days to live.	ο	0	0
2. In the hospital on intravenous medicines to keep you alive, with only days or weeks to live.	0	0	ο
3. At home requiring continuous medicine through an intravenous 24 hours a day with weeks to months to live.	ο	0	ο
4. At home and always breathless at rest and with light activities such as dressing or bathing.	0	0	ο
5. At home, comfortable at rest but breathless when walking around the house.	0	0	о
6. At home but breathless after walking more than one block or more than one flight of stairs	0	0	0
7. Not breathless during daily activities at home or after walking several blocks, but breathless with all other activities	0	0	ο

5. Prior to this survey, have you heard about a ventricular assist device (VAD)?

- A. Yes
- B. No
- C. Don't know
- 6. If you have heard about an assist device before, how did you first hear about a VAD?
 - A. Television/Radio
 - B. Newspaper/Magazine
 - C. Your health care provider
 - D. Family members or friends
 - E. The Internet

7. Knowing what you know now about different treatments for severe heart failure, which of these therapies would you rather have?

- A. Ventricular Assist Device
- B. Heart Transplant
- C. Don't know

8. Do you have a designated health care proxy or durable power of attorney for health care?

- A. Don't know
- B. Yes
- C. No

The next series of questions focuses on treatment choices near the end of life. Once again, all responses are confidential and will not be shared with your medical team. Please let us know if you wish to discuss any of these matters with your physicians.

9. Many life-sustaining therapies are available near the end of the life. These include dialysis, breathing machines, tubes for feeing, and whether or not you would wish to be resuscitated if your breathing or heart stops beating. Has your physician talked about your wishes regarding such life-sustaining therapies?

A. Yes

B. No

C. Don't know

10. At this time, if there are any life-sustaining therapies you do not want, please circle them below:

- A. Chest compressions
- B. Being placed on a breathing machine
- C. Kidney dialysis
- D. Transfer to the Intensive Care Unit (ICU)
- E. Feeding tube if unable to eat

Part IV: Missing Data Form

Check one response regarding WHY "self-report instruments" were not completed by the PATIENT:

- _____ too sick
- _____ too tired
- _____ too stressed, anxious, and / or depressed
- _____can't concentrate
- _____ no time / too busy
- _____ too much trouble / don't want to be bothered / not interested
- _____ unwilling to complete instruments, no reason given
- _____ unable to read English and / or illiterate
- _____ administrative (check specific reason below)
 - _____No time, coordinator too busy to administer self-report instruments
 - ____Coordinator forgot to administer self-report instruments
 - _____Unable to contact patient face-to-face or per telephone
 - Patient did not return mailed self-report instruments within the
 - window for instrument completion
 - _____ other reason

(describe)_____

Part V: Supplemental Questions:

1. In general, how comfortable would you be if your life depended on interacting with technology every day? Please draw an "X" on the line below that best describes how you feel.

Highly Uncomfortable

Very Comfortable

2. Treatments for heart disease can range from pills to pacemakers and even major heart surgeries. Some patients are willing to undergo more aggressive treatment to survive, while others are reluctant to consider more aggressive therapies and wish to focus on comfort alone. Based on how you feel today, please draw an "X" on the line below to indicate how you feel about medical treatments for your heart failure.

Focus on Comfort Only

Do Anything to Survive

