The patient survey instrument patient will assess quality of life, health-related stress, along with impression of and thresholds for consideration of VAD therapy. All survey responses are for research only and as such will be kept confidential and not be shared with members of the medical team. This written survey will be administered at Baseline A, Baseline B, the 12 month visit and again at the 24 month study close-out visit. Patients will receive the Kansas City Cardiomyopathy Questionnaire to determine disease specific quality of life and with the Euroqol-5D questionnaire including the thermometer. There will also be a brief instrument on health-related stress identical to

the tool being used in INTERMACS. The quality of life instruments will be completed independently by the patients in a single session.

After quality of life instruments have been completed, study coordinators will read a description of a VAD and provide a simple picture. The description of a VAD will include information on implantation, anticipated benefits and potential risks. The surveys will only be administered at face-to-face visits to allow a study nurse to assist with the VAD portion of the instrument. Patients will complete the VAD portion of the survey after receiving this standard information and a study nurse will be present to answer any queries about the VAD items. Similar VAD survey items were administered in the screening pilot with excellent response rates.¹⁷ Any patient who fails to complete a survey will have a missing data form filled outlining why the self-reported instruments were not completed. In all, there are 40 questions for the patients to answer in a written format, which should take approximately 35-40 minutes for most subjects. Original copies of the written survey instruments will be kept on site by study investigators and the data will be entered electronically by the coordinators or their data assistants on site (Appendix A).

Follow-up Telephone Contact at 6 and 18 Months

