A telephone call will be made by local site investigators or their study staff to patients at 6 and 18 months after study enrollment, but can be replaced by face-to-face visits if occurring as part of their routine care. The major purpose of this telephone call is to assess patient vital status and important interval events such as transplantation, placement of VAD, or other major procedures. The second purpose is to estimate the number of hospitalizations after study enrollment and the frequency of other major adverse events as recalled by patients. Any major endpoint or adverse event will be confirmed or amended by review of the interim medical record by site investigators. At the time of each study follow-up visit, the records will be reviewed for evidence of any major events leading to hospitalization that might have been missed in the intervening phone interviews.

Patients will be asked the questions determining functional class and profile. They will be asked a small subset of questions from the baseline questionnaire related to preferences for resuscitation and for VAD. They will be asked to bring their medications to the telephone to list them with doses.

Clinical Assessment at 12 months

It is anticipated that patients will be seen at some time between 10 and 14 months after the baseline study. Clinical information including routine laboratory values, physical examination, and symptoms will be reported. An echocardiogram and peak oxygen consumption will be recorded if obtained for clinical indications, as is routine practice for patients with this severity of illness followed at major centers. The six minute walk functional test will be repeated along with 5 meter gait speed to assess frailty. Patients will be re-administered the questionnaires regarding functional status, quality of life, and preferences for VAD as at baseline.

End of study at 24 months

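### VAD survey item 10 offers no 'none' or 'not sure' choice, so a blank is ambiguous and the share of patients refusing each life-sustaining therapy cannot be identified

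*Combined protocol and SAP*

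**What the plan says.** In Appendix A, Part III (MedaMACS VAD Survey), item 10 opens "At this time, if there are any life-sustaining therapies you" do not want, and continues "please circle them below". The list runs from A, "Chest compressions", to E, "Feeding tube if unable to eat", and stops there. The item just before it, "Has your physician talked about your wishes regarding such life-sustaining therapies", can be answered yes, no or don't know. Items 2, 3, 4, 5, 7 and 8 also have an unsure or don't-know choice.

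Section 6, Patient Survey, has the survey completed on paper at Baseline A, Baseline B, 12 months and 24 months. A study nurse is present for queries about the VAD items, and site staff key the data afterwards. On missing data it says: "Any patient who fails to complete a survey will have a missing data form filled outlining why the self-reported instruments were not completed". That form (Appendix A, Part IV) takes one reason and has no field for a single item.

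For the 6- and 18-month calls, section 6 says patients will be asked a "small subset of questions from the baseline questionnaire related to preferences for resuscitation and for VAD". It does not say which questions these are or how answers are recorded. Section 8 gives no coding rule for item 10 and leaves analysis plans for specific questions until later.

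**The concern.** The item records only objections. Someone with no objection has nothing to mark, and neither has someone who is undecided or who passed over the question. Once the form is collected, no analysis can separate the three.

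Aim 3 covers patients' preferences for their care. Within the VAD survey only items 9 and 10 touch on resuscitation, and item 9 asks whether a discussion took place, so item 10 is where the wish itself is recorded. It is asked at four visits. A blank followed by a circled answer may be a change of mind or only a change in whether the patient answered. If the item is also among those asked by telephone, a spoken yes, no or unsure would be set beside a paper form that cannot hold those answers.

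**Working it through.** The plan states no refusal rate, skip rate or estimate for item 10, so there is no figure to reproduce. Every rate below is an assumption, used to show direction and possible size.

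**Inputs (assumed)**
- r = true share who would refuse chest compressions (option A).
- s = share who skip the item, unrelated to their preference.
- q = share of those accepting compressions who would circle some other therapy.
- For simplicity, nobody is undecided.

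**1. Blank coded as 'refuses nothing'.** Estimate = r(1 − s).
- r = 0.20, s = 0.10: 0.20 × 0.90 = 18%, below the true 20%.
- r = 0.20, s = 0.05 to 0.20: 19% down to 16%.
- r = 0.30, s = 0.20: 0.30 × 0.80 = 24%, below the true 30%.
- s = 0: no bias.

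**2. Blank coded as missing on the current form.** Only patients who circled something remain, so the estimate = r(1 − s) / [r(1 − s) + (1 − r)q(1 − s)].
- r = 0.20, s = 0.10, q = 0.10: 0.18 / (0.18 + 0.072) = 71%.
- r = 0.20, s = 0.10, q = 0.30: 0.18 / (0.18 + 0.216) = 45%.
- r = 0.30, q = 0.10: 0.30 / (0.30 + 0.07) = 81%; with q = 0.30: 0.30 / (0.30 + 0.21) = 59%. The factor (1 − s) cancels.

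The two rules miss in opposite directions. The second misses by more because patients who accept everything leave the denominator.

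**3. What the form alone can establish.** Take r = 0.20, s = 0.10, q = 0.10. Option A is circled by 18%, only another option by 7.2%, and 100 − 18 − 7.2 = 74.8% are blank. Since s cannot be seen, the logical limits for refusal run from 18% to 18 + 74.8 = 92.8%. If a 'none' choice made the 10% who skipped visible, they would run from 18% to 18 + 10 = 28%, and the estimate among those who answered would be 20%. These are limits, not likely values.

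**4. Change between visits.** Hold r at 20% and let s fall from 20% to 5%. Under the first rule the estimate moves from 16% to 19%, an apparent rise of 3 points with no change in preference.

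**5. What the extra options do not cure.** If skipping depends on preference, the estimate among those who answer is still off: at r = 0.20, with 20% of refusers and 5% of others skipping, it is 0.16 / (1 − 0.04 − 0.04) = 17.4%. But the amount of skipping is then known.

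**The case against.** The item is conditional, so a patient with no objections who follows the instruction leaves it blank; a blank is a designed response. Items 8 and 9 need a mark, so a patient who stopped before item 10 can be noticed. A nurse is present, and section 6 reports that similar VAD survey items were well answered in the screening pilot. Part V, question 2 also asks about comfort versus survival. All of this suggests that skipping may be uncommon. It does not show which blanks are skips: patients who stop after item 9 or are undecided look like those who accept everything, no check for blanks is described, and the pilot remark gives no rate for this item.

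A reader might infer that refusal of resuscitation is underestimated. The documents do not support that. It would require blanks to be coded as no refusal and some skippers to be refusers; the plan states no coding rule, and coding blanks as missing pushes the estimate up.

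A reader might also infer that the resuscitation outcome in Aim 1.3 depends on item 10. The aim does not name it, and Appendix B collects code status separately under Events/Outcomes. That element records status, not the patient's confidential wish, so it does not repair item 10; but the outcome does not rest on item 10 either. Extending the problem to the telephone calls is conditional, because the questions used there are not specified.

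**Conclusion.** The point holds as a limited defect in one survey item. On the current form the share refusing each therapy, and its change over time, cannot be identified. The bias is downward if blanks are coded as no refusal and some skippers would have refused, and upward if blanks are coded as missing. Its true size is unknown: the percentages above rest on assumed refusal and skip rates, and with no skipping and no undecided patients the first rule would be unbiased.

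The consequence is confined to a descriptive preference measure. It does not affect the survival hypothesis, the composite endpoint, the sample size or the code status element. It is a minor improvement, worth making because it is nearly free and cannot be made up for after the forms are collected.

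**What to change.** - Add two choices to item 10: 'F. None – I would want all of these if needed' and 'G. Not sure'.
- Have the study nurse who is already present look for a blank before the visit ends and invite the patient to complete the item.
- If the item is asked at 6 and 18 months, use the same choices and record them in the same way.
- Code a blank that remains as missing, and report how many there are at each visit.
- Do not force a mark at data entry. The form is on paper and keyed later, so a forced mark could not come from the patient and would conflict with coding blanks as missing.

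The new choices and the coding rule must come in together, because coding blanks as missing on the present form would overstate refusal. The cost is two lines on the form and a brief check at each visit. Blanks on any forms completed before the change would stay ambiguous.
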